9.4.5. Safety Monitoring

The Lilly clinical pharmacologist will monitor safety data throughout the course of the study.

Lilly will review SAEs within time frames mandated by company procedures. The Lilly clinical pharmacologist will consult with the functionally independent Global Patient Safety therapeutic area physician or clinical research scientist when appropriate and periodically review:

- trends in safety data
- laboratory analytes
- AEs, including monitoring of rash

If a study subject experiences elevated ALT $\geq 3X$ ULN, ALP $\geq 2X$ ULN, or elevated total bilirubin $\geq 2X$ ULN, clinical and laboratory monitoring should be initiated by the investigator. Details for hepatic monitoring depend upon the severity and persistence of observed laboratory test abnormalities. To ensure subject safety and compliance with regulatory guidance, the investigator is to consult with the Lilly-designated clinical research physician regarding collection of specific recommended clinical information and follow-up laboratory tests ([Appendix 4](#)).

9.5. Pharmacokinetics

At the visits and times specified in the Schedule of Activities (Section 2), venous blood samples of approximately 2 mL each will be collected to determine the plasma concentrations of LY3337641. A maximum of 3 samples may be collected at additional time points during the study if warranted and agreed upon between both the investigator and sponsor. Instructions for the collection and handling of blood samples will be provided by the sponsor. The actual date and time (24-hour clock time) of each sampling will be recorded.

Drug concentration information that may unblind the study will not be reported to investigative sites or blinded personnel until the study has been unblinded.

9.5.1. Bioanalysis

Samples will be analyzed at a laboratory approved by the sponsor and stored at a facility designated by the sponsor.

Concentrations of LY3337641 will be assayed using a validated liquid chromatography-tandem mass spectrometry method. Analyses of samples collected from placebo-treated subjects are not planned.

Bioanalytical samples collected to measure IP concentrations will be retained for a maximum of 1 year following last subject visit for the study. During this time, samples remaining after the bioanalyses may be used for exploratory analyses such as additional metabolism and/or protein binding work.

9.6. Pharmacodynamics

At the visits and times specified in the Schedule of Activities (Section 2), venous blood of approximately 16 mL at each time point will be collected to determine free BTK and total BTK amount. Peripheral blood nuclear cells will be isolated. Lysates of the peripheral blood nuclear cells will be used to determine the concentrations of compound free BTK and total BTK using an enzyme-linked immunosorbent assay–based methodology.

The sample(s) will be stored for up to a maximum of 1 year after the last subject visit for the study at a facility selected by the sponsor.

9.7. Genetics

A blood sample will be collected for pharmacogenetic analysis as specified in the Schedule of Activities (Section 2), where local regulations allow.

Samples will not be used to conduct unspecified disease or population genetic research either now or in the future. Samples will be used to investigate variable exposure and response to LY3337641 and to investigate genetic variants thought to play a role in the perceived mechanism of action of LY3337641. Assessment of variable response may include evaluation of AEs or differences in efficacy.

All samples will be coded with the subject number. These samples and any data generated can be linked back to the subject only by the investigative site personnel.

Samples will be retained for a maximum of 15 years after the last subject visit, or for a shorter period if local regulations and/or ERBs (ethical review boards) impose shorter time limits, for the study at a facility selected by Lilly or its designee. This retention period enables use of new technologies, response to regulatory questions, and investigation of variable response that may not be observed until later in the development of LY3337641 or after LY3337641 is commercially available.

Molecular technologies are expected to improve during the 15-year storage period and therefore cannot be specifically named. However, existing approaches include whole genome or exome sequencing, genome wide association studies, multiplex assays, and candidate gene studies. Regardless of the technology utilized, data generated will be used only for the specific research scope described in this section.

9.8. Biomarkers

Biomarker research is performed to address questions of relevance to drug disposition, target engagement, PD, mechanism of action, variability of patient response (including safety), and clinical outcome. Sample collection is incorporated into clinical studies to enable examination of

these questions through measurement of biomolecules including DNA, RNA, proteins, lipids, and other cellular elements.

Serum, plasma, and/or whole blood RNA samples for nonpharmacogenetic biomarker research may be collected at the times specified in the Schedule of Activities (Section 2) where local regulations allow.

Samples will be used for research on the drug target, disease process, variable response to LY3337641, pathways associated with diseases related to the immune system, mechanism of action of LY3337641, and/or research method, or for validating diagnostic tools or assay(s) related to diseases related to the immune system.

All samples will be coded with the subject number. These samples and any data generated can be linked back to the subject only by the investigative site personnel.

Samples will be retained for a maximum of 15 years after the last subject visit, or for a shorter period if local regulations and/or ERBs impose shorter time limits, at a facility selected by Lilly. This retention period enables use of new technologies, response to regulatory questions, and investigation of variable response that may not be observed until later in the development of LY3337641 or after LY3337641 is commercially available.

9.9. Health Economics

This section is not applicable for this study.

10. Statistical Considerations and Data Analysis

10.1. Sample Size Determination

Up to 60 subjects may be enrolled so that approximately 36 to 48 subjects complete the study.

The sample size is customary for Phase 1 studies evaluating safety, PK, and/or PD parameters and is not based on the power of statistical hypothesis tests.

Subjects who are randomized but discontinue the study may be replaced in the same cohort and race (Japanese or Caucasian) at the discretion of the sponsor.

10.2. Populations for Analyses

10.2.1. Study Participant Disposition

All subjects who discontinue from the study will be identified, and the extent of their participation in the study will be reported. If known, a reason for their discontinuation will be given.

10.2.2. Study Participant Characteristics

Subjects' age, sex, weight, body mass index, height, race/subcategory, or other demographic characteristics will be recorded and summarized by treatment group as well as overall.

10.3. Statistical Analyses

Statistical analysis of this study will be the responsibility of Eli Lilly and Company or its designee.

PK analyses will be conducted for all subjects who receive at least 1 dose of LY3337641 and have evaluable PK data. PD analyses will be conducted on the full analysis set, which includes all data from all subjects receiving at least 1 dose of LY3337641 or placebo. Safety analyses will be conducted for all randomized subjects who receive at least 1 dose of LY3337641 or placebo and have at least 1 postdose safety assessment, regardless of whether they have completed all protocol requirements. For QT interval, all subjects with at least 1 postdose QT interval measurement will be included in the analysis.

Summary statistics, data tabulations, and data graphs will be provided and may be separated by race (Japanese and Caucasian) as appropriate.

Additional exploratory analyses of the data will be conducted as deemed appropriate. Study results may be pooled with the results of other studies for population PK/PD analysis purposes.

10.3.1. Safety Analyses

10.3.1.1. Clinical Evaluation of Safety

All IP and protocol procedure AEs will be listed, and if the frequency of events allows, safety data will be summarized using descriptive methodology.

The incidence of symptoms for each treatment will be presented by severity and by association with the IP as perceived by the investigator. Symptoms reported to occur prior to enrollment will be distinguished from those reported as new or increased in severity during the study. Each symptom will be classified by the most suitable term from the medical regulatory dictionary.

The number of IP-related SAEs will be reported.

10.3.1.2. Statistical Evaluation of Safety

Safety parameters that will be assessed include laboratory parameters, vital signs, and ECG parameters. The parameters will be listed and summarized using standard descriptive statistics. Prior to any statistical analysis of QT interval, QT values will be corrected for heart rate based on QTcF. The relationship between concentrations of LY3337641 and changes from baseline QTcF (Δ QTcF) will be explored to assess the effect of LY3337641 concentration on the Δ QTcF. A detailed analysis for QT interval will be provided in the Statistical Analysis Plan. Additional analysis will be performed if warranted upon review of the data.

10.3.2. Pharmacokinetic Analyses

10.3.2.1. Pharmacokinetic Parameter Estimation

PK parameter estimates for LY3337641 will be calculated by standard noncompartmental methods of analysis.

In the SD cohorts, the primary parameters for analysis will be C_{\max} , area under the concentration versus time curve from zero to infinity ($AUC_{0-\infty}$), and area under the concentration versus time curve from 0 to 24 hours (AUC_{0-24}) of LY3337641. In the MD cohorts, the primary parameters to be calculated will include C_{\max} (or C_{\max} during a dosing interval at steady state [$C_{\max,ss}$]) and area under the concentration versus time curve during the dosing interval ($AUC_{0-\tau}$) of LY3337641 after the first and last dose of IP. Other noncompartmental parameters, such as half-life, apparent clearance, apparent volume of distribution, and accumulation ratio (MD period only), may be reported.

Additional analysis may be conducted if appropriate.

10.3.2.2. Pharmacokinetic Statistical Inference

The dose proportionality of selected LY3337641 PK parameters, including log transformed C_{\max} and relevant AUC values will be examined for all subjects and for each population across the entire dose range using a power model approach (Smith et al. 2000) to estimate the slope of the power model, which represents the ratio of dose-normalized geometric means. Exploratory power model analysis based on the model including race and race-by-dose interaction terms will also be performed to examine the effect of the race on dose proportionality.

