3.3. Benefit/Risk Assessment

No clinically significant safety concerns have been identified at the doses proposed in this study for LY3337641. The dose levels included in this study are within the range of doses studied previously, and the tolerability has been confirmed.

More information about the known and expected benefits, risks, serious adverse events (SAEs) and reasonably anticipated adverse events (AEs) of LY3337641 are to be found in the Investigator's Brochure.

4. Objectives and Endpoints

Table JPDB.1 shows the objectives and endpoints of the study.

Table JPDB.1. Objectives and Endpoints

| Objectives | Endpoints |
|-------------------------------------------------------------------------------------------------------------------------------------------------------------------------------------------------------------------------------------------------------------------------------------------------------------------------------------------------------------------------------------------|---------------------------------------------------------------------------------------------------------|
| 
Primary To explore the safety and tolerability of LY3337641 in healthy Japanese and Caucasian subjects
 | AEs and SAEs |
| 
Secondary To estimate the PK parameters of single and multiple doses of LY3337641 following oral administration in healthy Japanese and Caucasian subjects
 | C _{max} and AUC |
| 
Exploratory Objectives 1. To explore the PD following single and multiple doses of LY3337641 in healthy Japanese and Caucasian subjects 2. To explore the safety, tolerability, PK, and PD of LY3337641 in Japanese subjects in relation to Caucasian subjects 3. To explore the effect of LY3337641 on ECG findings in healthy Japanese and Caucasian subjects
 | 
1. BTK occupancy 2. AEs, SAEs, C_{max}, AUC, and BTK occupancy 3. ECG parameters
 |

[figure not shown]
Abbreviations: AEs = adverse events; AUC = area under the plasma concentration-time curve; BTK = Bruton's tyrosine kinase; C_{max} = maximum drug concentration; ECG = electrocardiogram; PD = pharmacodynamics; PK = pharmacokinetic(s); SAEs = serious adverse events.

5. Study Design

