9.3.2 Pharmacokinetic Statistical Methodology

Dose proportionality among the 5 mg, 30 mg (Day 1), 80 mg and 160 mg dose levels will be assessed using a power model.

The PK parameters C_{max} , $AUC_{0-\infty}$, and AUC_{0-24} will be assessed separately using a power model as follows:

$$\log(PK_i) = \alpha + \beta_i \cdot \log(dose_i) + \varepsilon_i$$

where i represents the i th subject, PK represents a pharmacokinetic parameter (AUC or C_{max}), and ε_i is a residual error term. The dose proportionality will be reported as the estimated ratio of dose-normalized means

$$\hat{R}_{dnm} = \left(\frac{h}{l}\right)^{\hat{\beta}_1 - 1}$$

and its 90% CI, where h and l denote the highest and lowest doses included in the model, respectively. The estimates of β along with its 90% CI, predicted geometric mean, and ratio of dose normalized geometric mean will be reported for each parameter.

The following SAS code will be used:

```
proc mixed data=pk;
  by parameter;
  model lpk = ldose / alpha=0.1 residual ddfm=kr;
  estimate 'xx mg' intercept 1 ldose yy / cl;
  estimate 'zz mg - xx mg' ldose pp / alpha=0.1 cl;
  ods output solutionf=est;
  ods output estimates=estims;
run;
```

The above analysis will be repeated for Japanese and Caucasian subjects separately to examine the effect of the population on dose proportionality.

The PK summary tables and figures will be the responsibility of Eli Lilly and Company.

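### The plan sets out to relate Japanese to Caucasian exposure, but neither document plans a Japanese:Caucasian ratio of Cmax or AUC with a confidence interval

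*Protocol*

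**What the plan says.** Protocol Section 4, Table JPDB.1, gives exploratory objective 2 as "To explore the safety, tolerability, PK, and PD of LY3337641 in Japanese subjects in relation to Caucasian subjects", with endpoints "AEs, SAEs, C_{max}, AUC, and BTK occupancy". SAP 4.3 repeats the objective.

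For PK inference, Protocol 10.3.2.2 fits the power model overall and in each population. It then adds an exploratory power model "including race and race-by-dose interaction terms will also be performed to examine the effect of the race on dose proportionality". That is the only purpose stated for it.

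SAP 9.3.2 has no race term for PK. Its model line is "model lpk = ldose / alpha=0.1 residual ddfm=kr", and race is handled by refitting: "The above analysis will be repeated for Japanese and Caucasian subjects separately to examine the effect of the population on dose proportionality". The outputs include the slope with its 90% CI, and "predicted geometric mean, and ratio of dose normalized geometric mean will be reported for each parameter". The code obtains predictions at named doses through "estimate 'xx mg' intercept 1 ldose yy / cl".

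SAP 9.1 provides summaries by population, with geometric means and geometric CV% for AUC and Cmax. SAP 3 says that the SAP supersedes the protocol's statistical section. SAP 11 reports no changes from the protocol's analyses.

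**The concern.** A slope comparison and an exposure comparison answer different questions. If Japanese exposure is the same multiple of Caucasian exposure at every dose, the two log-log lines are parallel. The slopes then agree exactly, whatever the multiple is. Objective 2 is about the distance between the lines, and no listed output states that distance with its uncertainty.

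This bears on the study's use. Protocol 5.4 says that the trial is run to support including Japanese subjects in later studies. A team reading the report would want one estimate of relative exposure and its precision. Under the plan they would have to divide predicted means from two separate fits and work out an interval themselves.

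The two documents also disagree. The protocol's joint race model is absent from the SAP, and the SAP does not record its removal.

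**Working it through.** **Check on the design.** The planned number of completers (36 to 48) follows from the cohort sizes: 12 + 3 × 8 = 36 without optional Cohort 5, and 2 × 12 + 3 × 8 = 48 with it. The documents contain no power calculation to reproduce.

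**Inputs.** Active subjects come from Protocol 5.1, and the doses in the power model from SAP 9.3.2 (30 mg is Day 1):

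| Dose (mg) | Japanese | Caucasian |
|---|---|---|
| 5 | 3 | 3 |
| 30 | 6 | 3 |
| 80 | 3 | 3 |
| 160 | 3 | 3 |
| Total | 15 | 12 |

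The confidence level is 90%, as in SAP 9.3.2. The between-subject SD of log exposure, σ, is not in the documents. I assume 0.3 and show 0.25 to 0.5.

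**1. What the slope shows.** I generated noise-free data with slope 1 and a constant ratio of 1.3, and fitted race, log dose and their interaction. The race term is 0.2624 = ln 1.3 and the interaction is 0. The whole difference lies in the level and none of it in the slope.

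**2. Common-slope model.** `log(PK) = alpha + gamma × race + beta × log(dose)`. Mean log dose is 3.574 in Japanese and 3.617 in Caucasian subjects, and the within-race sums of squares of log dose are 20.48 and 20.37. Hence

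`Var(gamma) = σ² × [1/15 + 1/12 + (3.574 − 3.617)²/(20.48 + 20.37)] = 0.1500 σ²`

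so SE = 0.387σ on 27 − 3 = 24 df, with t = 1.711.

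- σ = 0.3: SE 0.116, and exp(1.711 × 0.116) gives a factor of 1.22.
- σ = 0.25: factor 1.18.
- σ = 0.5: factor 1.39.

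**3. Race-by-log(dose) model, evaluated at each studied dose.** The variance of the log ratio at dose d is

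`σ² × [1/15 + (ln d − 3.574)²/20.48 + 1/12 + (ln d − 3.617)²/20.37]`

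on 23 df, with t = 1.714.

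| Dose (mg) | SE/σ | SE at σ = 0.3 | 90% CI factor |
|---|---|---|---|
| 5 | 0.732 | 0.220 | 1.46 |
| 30 | 0.392 | 0.118 | 1.22 |
| 80 | 0.459 | 0.138 | 1.27 |
| 160 | 0.604 | 0.181 | 1.36 |

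**4. Recovering the ratio from the SAP's own output.** In simulated data, the quotient of the two by-race predicted geometric means equalled the interaction-model ratio at 5, 30 and 160 mg. The point estimate can therefore be recovered from the planned output. What is not planned is the contrast and its interval.

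**5. Day 15, 6 v 3 at 30 mg.** SE = σ × √(1/6 + 1/3) = 0.707σ on 7 df, with t = 1.895. The factor is 1.49 at σ = 0.3 (1.40 at 0.25, 1.95 at 0.5).

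**The case against.** The strongest reply is that the plan already carries most of this information. SAP 9.3.2 reports predicted geometric means, its code requests confidence limits at named doses, and the analysis is repeated in each race on all 15 and all 12 active subjects. SAP 9.1 adds by-race geometric means and CV%. Objective 2 says only that PK will be explored in relation to Caucasian subjects and names no ratio, interval or method. It is exploratory, the sample size is not based on power, and Protocol 10.3 allows further exploratory analyses. All of that stands. It makes this a gap in reporting and precision: objective 2 is still addressed descriptively.

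Three stronger readings might be inferred, and the documents support none of them.

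- *That the data are used only for slopes.* They are not, because predicted means by dose and race are a planned output.
- *That a constant difference in exposure would go unseen.* It would shift every Japanese predicted mean against its Caucasian counterpart. Only the slope comparison would miss it.
- *That the race effect would be read at 1 mg, where log dose is zero.* This would need race terms added to an uncentred model and the bare coefficient reported. Protocol 10.3.2.2 states neither the parameterization nor such a report, and the SAP has no PK race term. The SAP's own practice is to estimate at named doses.

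Nor does the common-slope model gain much over the protocol's joint model at 30 mg, where the factor is 1.22 under either. What is missing is an explicit contrast, since the data already hold the information.

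**Conclusion.** The point holds as an improvement worth considering. Neither document plans a Japanese:Caucasian ratio of Cmax or AUC with an interval. The stated aim of both race analyses is dose proportionality, which cannot by itself answer objective 2. The SAP also drops the protocol's joint race model without recording it as a change.

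The planned data would support a common ratio with a 90% CI of times or divided by 1.22 at an assumed log SD of 0.3 (1.18 to 1.39 over 0.25 to 0.5), and 1.22 to 1.46 at the individual studied doses at SD 0.3. These figures rest on that assumed SD, on complete data from 27 active subjects without Cohort 5, and, for the single ratio, on a common slope. They describe precision only. The study is unpowered and they should not be read as a criterion that it must meet. No stated figure in the plan is in error.

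**What to change.** In SAP 9.3.2, and in Protocol 10.3.2.2 if it is amended:

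1. For Cmax, AUC0-24 and AUC0-∞ in all active subjects, fit `log(PK) = alpha + gamma × race + beta × log(dose)`. Report exp(gamma) with its 90% CI as an exploratory Japanese:Caucasian geometric mean ratio, with no acceptance limit.
2. Restore the race-by-log(dose) model as the check on the common slope, and report the ratio from it by ESTIMATE statements at 5, 30, 80 and 160 mg.
3. For Day 15 Cmax,ss and AUC0-τ, report the 6 v 3 ratio with its 90% CI.
4. Reconcile Protocol 10.3.2.2 with SAP 9.3.2 and SAP 11, so that the joint model is either specified or recorded as a change.

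The cost is a few lines of text and code, with no new data. The one small downside is that the overall ratio assumes a common slope, which step 2 examines.

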10.3.3. Pharmacodynamic Analyses

BTK occupancy will be listed and summarized using standard descriptive statistics. Additional analysis will be performed if warranted upon review of the data.

10.3.4. Pharmacokinetic/Pharmacodynamic Analyses

Exploratory graphical PK/PD analyses may be conducted to evaluate the relationship between LY3337641 concentrations (or exposure) and PD measures. Additional model-based analyses may be conducted if deemed appropriate.

10.3.5. Interim Analyses

The Lilly study team is unblinded. Data may be analyzed while the trial is ongoing, but no changes to the study design are planned. An assessment committee will not be formed.

Up to 3 interim analyses are planned to occur during the study according to the following timeframe: when at least safety and PK data of (1) Day 2 predose (24 hours after first dose) become available from at least 11 subjects in Cohort 1, including at least 4 Caucasian subjects; (2) Day 17 (48 hours after last dose) become available from Cohort 1; and (3) Day 29 become available from Cohort 1. All safety and PK data available from other cohorts by this time will be included in the interim analysis. The purpose of the interim analysis is to support the inclusion of Japanese subjects in future studies. The investigator and the Lilly clinical pharmacologist will review the safety and tolerability data, and the PK/PD scientist will review the PK data. The investigator will remain blinded, and the Lilly study team will be unblinded during this interim review.

Information that may unblind the study during the analyses will not be reported to study site or blinded personnel until the study has been unblinded.

Additional interim analysis may be conducted at any time throughout the study as required to ensure subject safety or to help guide dosing.

If an unplanned interim analysis is deemed necessary, the Lilly clinical pharmacologist, clinical research physician/investigator, or designee will consult with the appropriate medical director or designee to determine if it is necessary to amend the protocol.

11. References

- Burger JA. Bruton's tyrosine kinase (BTK) inhibitors in clinical trials. *Curr Hematol Malig Rep*. 2014;9(1):44-49.
